5.2 Study design

This is a multicenter, randomized, double-blind, active-controlled, double-dummy, parallel group comparative study.

(1) Screening period

The screening period begins on the first day of the screening period, and ends upon completion of tests required on the first day of the treatment period. Maximum screening period time is 6 weeks. Two visits will be made during the screening period; the first (SV1) is the first day of the screening period. The second screening period visit (SV2) occurs after results from laboratory tests performed on the first day of the screening period have been obtained. Testing may be repeated as necessary.

(2) Treatment period

The treatment period will last from completion of scheduled tests on the first day of the treatment period to completion of blood sampling for haematology tests on the final day of the treatment period (Week 52 of the treatment period or discontinuation of treatment).

The treatment period consists of phase 1 and phase 2, as defined below.

- ✓ Treatment period Phase 1: From completion of scheduled tests for the first day of the treatment period to completion of scheduled tests for Week 24 of the treatment period. Treatment period Phase 1 will be double-blind.
- ✓ Treatment period Phase 2: From the completion of the tests specified for Week 24 of the treatment period to the completion of tests specified for Week 52 of the treatment period. Even after all subjects complete the treatment period Phase I and the key

code is opened, the subjects, study institution staff members, and monitoring personnel will remain blinded to treatment. Details of the procedure of maintaining the blindness will be separately defined before opening of the key code.

During the treatment period, subjects are to visit the study site on the day of dialysis after a 2-day interdialytic interval; however, if this is difficult, subjects are to visit the study site on the day of dialysis after a 1-day interdialytic interval. After the first day of the treatment period, subjects are to visit the study site every 2 weeks until Week 12 and every 4 weeks after Week 12 to undergo the scheduled test. However, subjects are to visit the study site at shorter intervals as necessary, if excessive increases or decreases in Hb are of concern based on the time course of Hb levels, the dose interval of darbepoetin alfa injection is shorter than the scheduled visit interval, or for hemodialysis.

(3) Follow-up observation period

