- [a] The screening period can be up to 6 weeks. Test results should be reviewed prior to transition from the first day of the screening period to screening period Visit 2 and from screening period Visit 2 to the first day of the treatment period. Re-testing can be performed as necessary.
- [b] The scheduled study visit during the treatment period shall be the dialysis day 2 days after the previous dialysis, and if it is difficult, the dialysis day 1 day after the previous dialysis.
- [c] Should not be performed if discontinued before the treatment period.
- [d] Fundoscopy and chest X-ray should be performed once during the screening period. Fundoscopy and chest X-ray should be performed once during Weeks 20–24 of the treatment period, and once during Weeks 48–52 of the treatment period. Should be performed within 14 days after discontinuation whenever possible if discontinued during the treatment period.
- [e] Body weight should be measured before and after dialysis.
- [f] Measurements on the day of dialysis should be performed before dialysis during the screening period.
- [g] Tests during the treatment period should be performed before dialysis on the day of dialysis.
- [h] To be performed only in female subjects of childbearing potential.
- [i] Hb values should be measured in blood collected in the supine position.
- [j] Only Hb values should be measured.
- [k] Only urea nitrogen values will be measured before and after dialysis on the first day, Week 24, and Week 52 of the treatment period and on the day of treatment discontinuation.
- [l] Measurements should be made before blood sampling as much as possible. Measurements should be made in the sitting position after 5 minutes of rest.
- [m] Measurements should be made before blood sampling as much as possible. Measurements should be made in the supine position after 5 minutes of rest.
- [n] AE investigation should begin after study drug administration.
- [o] Blood should be collected once as early as possible after Week 2 of the treatment period for subjects who have given consent to the genetic analysis tests.
- [p] For subjects giving consent to the plasma protein binding rate study, blood should be collected once before study drug administration. Blood collection should be performed before dialysis on the day of dialysis.

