## 4.10 Mean daily dose/mean weekly dose

Mean daily dose of MT-6548 during each scheduled study visit period\* = Daily dose based on the physician's prescription  $\times$  Period of administration (days)\*3 of the corresponding dose\*2 between the scheduled study visits\*/Period between the scheduled study visits (days)\*4

Mean weekly dose of darbepoetin alfa during each scheduled study visit period\* = Daily dose based on the physician's prescription  $\times$  Period of administration (days)\*5 of the corresponding dose\*2 between the scheduled study visits\*/Period between the scheduled study visits (days)\*4  $\times$  7

\*: For each period between the scheduled study visits, the actual study visit dates will not be considered, and this variable should be fixed as follows:

- ✓ The first day of the treatment period to Week 2 of the treatment period: The first day of the treatment period (Day 1) to 14 days

- ✓ Week 2 of the treatment period to Week 4 of the treatment period: Day 15 to Day 28
- ✓ The same should apply thereafter, and the final period between the scheduled study visits should be Week 48 to Week 52 of the treatment period: Day 337 to the day before the day of blood sampling for hematology tests at Week 52 of the treatment period. However, for subjects who discontinued their treatment, the final period between the scheduled study visits should be up to the day before discontinuation.

\*2: If there are multiple applicable doses, the sum of the calculated values for each dose should be used.

\*3: The number of days without drug administration other than drug interruption should not be excluded from the “period of administration (days).”

\*4: 14 days up to Week 12 of the treatment period and 28 days after Week 12 of the treatment period. However, for subjects who discontinued their treatment, the final period between the scheduled study visits (days) should be the actual number of days until the day before discontinuation.

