#### 4.13 Iron supplement dosage

The dose of iron supplements is defined by the following formula. However, the dose of iron supplements will not be calculated if iron supplements are used as needed.

Mean monthly dose of iron supplements during the screening period\* and each scheduled study visit period\* (tabulation period of iron supplements) = (Daily dose based on the physician’s prescription  $\times$  Period of administration (days) of the corresponding dose during the tabulation period of iron supplements)/Tabulation period of iron supplements (days)  $\times$  30.4375

\*: The number of days of the screening period is “First day of the treatment period – First day of the screening period.”

\*2: For each period between the scheduled study visits, the actual study visit dates are not considered, and this tabulation is fixed as follows:

- ✓ The first day of the treatment period to Week 2 of the treatment period: The first day of the treatment period (Day 1) to Day 14
- ✓ Week 2 of the treatment period to Week 4 of the treatment period: Days 15 to 28
- ✓ The same should apply thereafter, and the final period between the scheduled study visits should be Week 48 to Week 52 of the treatment period: Day 337 to the day before the day of blood sampling for hematology tests at Week 52 of the treatment period. However, for subjects who discontinued their treatment, the final period between the scheduled study visits should be up to the day before discontinuation.

\*3: If there are multiple applicable doses, the sum of the calculated values for each dose should be used.

\*4: For subjects who discontinued their treatment, the final period between the scheduled study visits (days) should be the actual number of days until the day before discontinuation.

\*5: In this tabulation, 1 month is counted as 30.4375 days (365.25/12 = 30.4375).

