Descriptive statistics of the change in the mean dose of iron supplement per month from the baseline (mean dose of iron during the screening period) should be calculated, after the first day of the treatment period, in each period between scheduled study visits and during the entire treatment period from the first day to Week 52 of the treatment period. Before and after comparison should be conducted for changes from baseline using the paired t-test. The changes should be compared between groups using the Student-t test. The mean value of the between-group difference (MT-6548 – darbepoetin), its 2-sided 95% CI, and p-value should be provided. The dosage of iron supplement should be calculated using the dose as iron. If no iron supplement is administered, the dose should be tabulated as 0 mg. Subjects who changed the administration route of an iron supplement during the treatment period and subjects who had never received an iron supplement during the treatment period should be excluded from the tabulation.

(6) Proportion of subjects receiving oral, intravenous, or iron supplement (any route)

The number, proportion, and 95% CI (Clopper-Pearson [Exact] method) of the proportion of subjects treated with oral, intravenous, or oral iron supplement (any route) should be provided by treatment group for the screening period, and after the first day of the treatment period, in each period between scheduled study visits and during the entire treatment period from the first day to

Week 52 of the treatment period. A McNemar tests should be used for before and after comparison between baseline (ratio of subjects receiving iron supplements by the aforementioned route in the screening period) and each period between scheduled study visits. The estimate, its 95% CI (exact method), and p-value (Fisher's exact test) for between-group difference (MT-6548 – darbepoetin) should be calculated for the proportion of subjects receiving oral, intravenous, or (any route) iron supplement.

Subjects who have not received an iron supplement are to be subjects who have never received an iron supplement during the relevant period, and subjects who have received an oral, intravenous, or (any route) iron supplement are to be subjects who have received an iron supplement at least once during the relevant period.

(7) Proportion of subjects with serum ferritin  $\geq 100$  ng/mL or TSAT  $\geq 20\%$ .

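### Iron use is counted as one dose or more in a period, but the within-arm McNemar tests compare periods of unequal length, so unchanged intermittent iron use can show a false change from baseline

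*SAP*

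**What the plan says.** Final SAP section 8.5.2 (6) tabulates the proportion of subjects on oral, intravenous or any iron, by arm, for screening, for each between-visit period and for the whole 52 weeks. Users "are to be subjects who have received an iron supplement at least once during the relevant period".

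The within-arm test is stated as: "A McNemar tests should be used for before and after comparison between baseline", where baseline is the "ratio of subjects receiving iron supplements by the aforementioned route in the screening period) and each period between scheduled study visits" supply the comparison. The arms are compared by a difference with exact interval and a Fisher p-value.

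The window lengths are found elsewhere:
- **Screening.** Protocol section 5.2: "Maximum screening period time is 6 weeks". No minimum is given. SAP section 4.13 counts each subject's actual days, from first screening day to first treatment day.
- **Treatment intervals.** SAP section 4.10, note 4: "14 days up to Week 12 of the treatment period and 28 days after Week 12 of the treatment period". That note concerns study drug dose. Section 4.13 starts the iron dose intervals with the same fixed days (1 to 14, then 15 to 28), and the visit schedule in Protocol section 5.2 gives the same lengths.

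The Phase 1 SAP, section 8.5.3 (6), uses the same definition and test up to Week 24. Neither SAP matches the windows or comments on their length.

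**The concern.** A count of subjects with one dose or more rises with the length of the window whenever dosing is intermittent. The SAP allows for this in the companion endpoint: the monthly iron dose in section 4.13 is divided by period days and scaled to 30.4375 days. The proportion, built from the same records, is not adjusted.

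Intermittent use is foreseeable. Protocol section 8.5.2 has iron given to maintain ferritin or TSAT, with dose and route left to the investigator. SAP section 4.13 provides for as-needed use, and intravenous iron is a separate category in the table.

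At stake is the interpretation of iron use after the switch of treatment. A within-arm p-value for a fall or rise from screening could be read as a drug effect on iron need when it reflects only window length.

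**Working it through.** **Plan's own figure.** None exists for this endpoint. The only design figure, above 95% for the primary analysis, reproduces: the standard error is 1.73 × √(2/150) = 0.200, and Φ(0.75/0.200 − 1.96) = 96.4%. It has no bearing on the iron table.

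**Inputs from the documents.** 150 per arm; two-sided 5%; screening up to 42 days; intervals of 14 and 28 days. **Assumed:** the dosing pattern, the share of intermittent users and the actual screening length.

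**Step 1: chance of being counted as a user.** With one dose every T days at random phase, P = min(1, L/T) for a window of L days.

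| Dosing gap T | 14-day window | 28-day window | 42-day window |
|---|---|---|---|
| daily or weekly | 100% | 100% | 100% |
| 28 days | 50% | 100% | 100% |
| 42 days | 33% | 67% | 100% |
| 56 days | 25% | 50% | 75% |

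With random dosing averaging one dose a month, P = 1 − exp(−L/30.4375), which gives 37%, 60% and 75%. The pattern does not depend on strict regularity.

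**Step 2: McNemar against the 14-day interval directly after screening.** Use is unchanged, every 28 days, in 10% or 20% of 150 subjects (15 or 30 expected); all others are concordant. With b pairs screening-only and c pairs interval-only, exact p = 2 × P(Bin(b + c, 0.5) ≤ min(b, c)), capped at 1. Six pairs against none give 2 × 0.5⁶ = 0.031; five give 0.063.

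| Screening | Share b / c of intermittent users | Expected b v c (10%; 20%) | Trials rejecting (10%; 20%) |
|---|---|---|---|
| 42 days | 50% / 0% | 7.5 v 0; 15 v 0 | false fall 77%; 99.8% |
| 21 days | 50% / 25% | 7.5 v 3.75; 15 v 7.5 | false fall 12%; 27% |
| 14 days | 50% / 50% | 7.5 v 7.5; 15 v 15 | under 2% each way |
| 7 days | 25% / 50% | 3.75 v 7.5; 7.5 v 15 | false rise 11%; 29% |

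Rejection rates are from 5,000 simulated trials per row. Exact enumeration agrees to about one percentage point: 76.6% and 99.8% at 42 days; 12.3% and 27.6% at both 21 and 7 days. For later 14-day intervals the net shift is the same but the split between b and c differs, so these rates belong to the first interval.

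**Step 3: after Week 12.** The same users count in 50% of 14-day intervals and 100% of 28-day intervals. With 15 to 30 such subjects, the counted users rise by 7.5 to 15 of 150, or 5 to 10 percentage points, whatever the screening length. McNemar against a 28-day interval then gives a false rise in 17% to 77% of trials with 21-day screening and 77% to 99.7% with 14-day screening. With 28- or 42-day screening there are no discordant pairs.

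**Step 4: equal windows.** 14 against 14 days rejects in about 1.5% of trials in each direction. 28 against 28 days gives no discordant pairs.

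**The case against.** The strongest reply is that the plan already holds a sound comparison. Both arms share the same treatment intervals and randomisation should balance screening length, so the Fisher comparison within an interval is not biased by window length. McNemar is not restricted to one arm here, so the same artefact would be expected to show under darbepoetin. The length-scaled monthly dose is analysed alongside. The endpoint is sixth among the other endpoints, and the Phase 1 SAP (section 8.5.4.7) calls such analyses exploratory. All of this stands, and it sets the priority.

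Three stronger readings are tempting, and the documents do not support them.
- *That the within-arm p-values are invalid as a class.* They mislead only when iron is intermittent and the windows differ. Continuous oral iron is unaffected.
- *That iron use will appear to fall after switching.* This needs screening longer than 14 days. At 14 days the bias vanishes, and at 7 days it reverses.
- *That one worked example gives the size.* With 22 subjects on 28-day iron and screening of 28 days or more, 11 pairs against 0 give p = 0.001. The same 22 with 21-day screening give about 11 against 5 or 6, p = 0.21 to 0.33; with 14-day screening, 11 against 11, p = 1.

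The reply does not remove the point. The SAP still asks for a test that can reject with no change in use, in a direction set by screening length.

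**Conclusion.** The concern holds for the within-arm McNemar tests and for reading the proportion across Week 12. It does not extend to the randomised comparison or the primary result. Under unchanged 28-day dosing in 10% to 20% of 150 subjects, the early artefact runs from a near-certain false fall (42-day screening), through none (14 days), to a false rise in about 11% to 29% of trials (7 days). The step up after Week 12 arises at any screening length.

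These sizes rest on an assumed regular schedule, an assumed share of users and one screening length for everyone. Real lengths will be mixed and may partly cancel. If nearly all iron is given at least weekly, the effect is negligible. Priority is low to moderate.

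**What to change.** 1. In final SAP section 8.5.2 (6), run McNemar only between windows of equal length, from recorded data. For example, compare the last 14 days of screening with each 14-day interval to Week 12, with a stated rule for subjects with shorter screening and a count of them. Alternatively, compare user status on the first treatment day with status on each visit day, defining what counts as on iron between intermittent doses.
2. Otherwise drop this McNemar test and rely on the between-arm comparison and the monthly dose. The dose is only a partial substitute: section 8.5.2 (5) excludes never-users and subjects who changed route, and section 4.13 omits as-needed use.
3. For the time course, merge the early intervals into 4-week blocks (Days 1–28, 29–56, 57–84), or footnote the change in interval length at Week 12.
4. Do not restrict the test to subjects with at least 28 days of screening. Re-testing for Hb, ferritin or TSAT (Protocol section 3.4) lengthens screening, so that would select on iron status.
5. Leave the re-tabulation in final SAP section 8.7.2 on the Phase 1 method. Its purpose is to isolate the effect of the changed data.

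The cost is SAP wording and re-binning; screening iron is already in the case report form (Protocol section 8.5.4). Merging loses 2-week resolution before Week 12.

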- (3) Set to ensure patients stable on hemodialysis or hemodiafiltration with reference to the “Guidelines for Clinical Evaluation of Therapeutic Drugs” for Renal Anemia (PFSB/ELD Notification No. 0930-2).
- (4) ESA type, route of administration, and dose interval were restricted in order to control Hb value fluctuations. ESA dosage may be adjusted to maintain Hb levels as required, but the upper limit of dosage was set because only patients whose dosage does not exceed the normal maintenance dosage described in the package insert are eligible for the study.
- (5) Set to ensure patients with controlled Hb with reference to target Hb values in nephrogenic anaemia therapy in the JSDT’s “Guideline for Renal Anemia in Chronic Kidney Disease 2015”.
- (6) Set to ensure appropriate efficacy evaluation by targeting patients without significant fluctuations in Hb levels.
- (7) Set to ensure patients without iron insufficiency, using as reference criteria for initiating iron supplementation therapy according to the JSDT’s “Guideline for Renal Anemia in Chronic Kidney Disease 2015.”
- (8) Set to ensure appropriate efficacy evaluation by targeting patients without insufficiencies in folic acid or vitamin B₁₂, required for hematopoiesis.

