9.2.3 Efficacy endpoints

Blood sampling will be performed at each study center for measurement by the contract laboratory testing facility. Study centers will store test reports issued by the contract testing laboratory. EPO measurements will be disclosed to the sponsor after key code opening, but will not be disclosed to subjects, study center staff, or monitoring staff until completion of the final data lock at the end of the study.

During the screening period, blood will be collected before dialysis whenever the subject makes a study visit on the same day they are scheduled for dialysis. During the treatment period, blood will be collected before dialysis on days the subject is scheduled for dialysis.

(1) Hb value

Blood sampling and Hb measurement will be performed in the supine position on the first day of the screening period, screening period Visit 2, the first day of the treatment period, Weeks 2, 4, 6, 8, 10, 12, 16, 20, 24, 28, 32, 36, 40, 44, 48, and 52 of the treatment period, and the day of discontinuation of treatment.

(2) Ratio of subjects who received ESA rescue therapy

If ESA rescue therapy is performed, type of ESA formulation used, administration route, dose interval, and dosage will be recorded in the CRF.

(3) Ratio of subjects who received red blood cell (RBC) transfusion rescue therapy.

If RBC transfusion rescue therapy is performed, type of RBC formulation used and dosage will be recorded in the CRF.

(4) Study drug dosage

Study drug dosage will be recorded in CRFs.

(5) Total number of dosage adjustments

Yes/no for MT-6548 dosage adjustments and post-adjustment dosage will be recorded in the CRF.

(6) Quantity of iron administered

Iron dosage will be recorded in CRFs.

(7) Iron-related measures (serum iron, TIBC, TSAT, and serum ferritin)

Blood sampling and measurement will be performed for serum iron, TIBC, TSAT, and serum ferritin on the first day of the screening period, the first day of the treatment period, Weeks 2, 4, 6, 8, 10, 12, 16, 20, 24, 28, 32, 36, 40, 44, 48, and 52 of the treatment period, and the day of discontinuation of treatment.

(8) Hepcidin

Blood sampling and measurement of hepcidin will be performed on the first day of the treatment period, treatment period Weeks 2, 4, 6, 12, 24, 36, and 52, and the day of discontinuation of treatment.

(9) Haematocrit, RBC count

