## 2.4 Rationale for sample size

A total of 300 subjects (150 each for the MT-6548 and darbepoetin groups) should be enrolled in the treatment period.

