### 8.1 Basic matters

#### 8.1.1 Level of significance and confidence coefficient

When implementing tests, level of significance should be set at 2-sided 5%. Confidence interval will be 2-sided with a confidence coefficient of 95%.

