The number, proportion, and 95% CI (Clopper-Pearson [exact] method) of the proportion of subjects with serum ferritin levels of  $\geq 100$  ng/mL or TSAT levels of  $\geq 20\%$  should be provided at each evaluation time point of the treatment period for each treatment group. A McNemar tests should be used for before and after comparison between baseline (ratio of subjects receiving iron supplements by the aforementioned route in the screening period) and each period between scheduled study visits. The estimate, its 95% CI (exact method), and p-value (Fisher's exact test) for between-group difference (MT-6548 – darbepoetin) should be calculated for the proportion of subjects with serum ferritin  $\geq 100$  ng/mL or TSAT  $\geq 20\%$ .

(8) Changes and rate of changes in iron-related indices (serum iron, TIBC, TSAT, and serum ferritin levels) and hepcidin from the first day of the treatment period

Iron-related indices (serum iron, TIBC, TSAT, and serum ferritin) and hepcidin should be measured at each evaluation time point of the treatment period, and their changes and rate of changes should be calculated from the first day of the treatment period to each evaluation time point of the treatment period. Descriptive statistics of the measurements, changes, and rate of changes should be calculated for each treatment group. A paired t-test should be performed for before and after comparison of changes and change rates from the first day of the treatment period.

A group comparison should be conducted for the change in iron-related indices (serum iron, TIBC, TSAT, and serum ferritin) and hepcidin from the first day of the treatment period to each evaluation time point using the MMRM model (with compound symmetry [CS] for within-subject variance-covariance matrix). LSMean, its standard errors, and 2-sided 95% CI should be calculated, and the point estimate, its standard errors, 2-sided 95% CI, and p-value should be provided for the group difference (MT-6548 – darbepoetin) of the LSMean by treatment group. Only the serum ferritin value at each evaluation time point of the treatment period should be similarly compared between groups.

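### The McNemar sentence for iron sufficiency (item 7 in both SAPs) is item 6's sentence on iron use, so it does not test change in iron sufficiency

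*SAP*

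**What the plan says.** The endpoint is item (7) in final SAP section 8.5.2 and in Phase 1 SAP section 8.5.3: the proportion of subjects with serum ferritin ≥100 ng/mL or TSAT ≥20%. The number, proportion and Clopper-Pearson interval "should be provided at each evaluation time point of the treatment period for each treatment group".

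The next sentence adds a within-arm test: "A McNemar tests should be used for before and after comparison between baseline". A parenthesis defines that baseline as the "ratio of subjects receiving iron supplements by the aforementioned route in the screening period", and the comparison is with "each period between scheduled study visits". The paragraph closes with a between-group estimate, exact interval and Fisher's test, which do name the ferritin/TSAT criterion.

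The same McNemar sentence stands in item (6) of both SAPs. There the endpoint is receipt of oral, intravenous or any-route iron, and the results are tabulated by period.

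The protocol, section 9.2.3 (7), provides the laboratory data: "Blood sampling and measurement will be performed for serum iron, TIBC, TSAT, and serum ferritin on the first day of the screening period". The same sentence goes on to list the first day of the treatment period and every treatment visit.

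**The concern.** McNemar's test asks whether one binary attribute, measured twice on the same subjects, has changed in frequency. In item (7) the attribute should be iron sufficiency. The baseline actually written is a treatment exposure, iron use in screening. Item (7) also has no route to which the reference to an aforementioned route could point, and it is measured at visits rather than over periods.

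A programmer following the text would produce, at every visit and in both arms, a p-value that cannot be read as evidence for or against a change in iron sufficiency. A reader of the tables would have no means of knowing that.

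**Working it through.** **Comparing the text**

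- Item (6): endpoint is iron use by route, the unit is the period between visits, and baseline is iron use in screening. These are consistent.
- Item (7): endpoint is ferritin/TSAT status and the unit is the evaluation time point. The McNemar sentence keeps item (6)'s baseline and item (6)'s periods. Neither fits.
- The SAPs have suitable wording elsewhere. For the Hb target range (final SAP 8.5.1 (3), Phase 1 SAP 8.5.2 (2)), McNemar compares status on the first day of the treatment period with status at each evaluation time point. Item (8) also takes the first day of the treatment period as its baseline for ferritin and TSAT.
- The errata supplied with the SAPs correct comparable drafting slips in neighbouring items but leave this sentence alone.

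The sentence never names the follow-up variable, so there are two readings.

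**Reading A: follow-up is iron use.** The test then duplicates item (6), and iron sufficiency has no before-after test.

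**Reading B: follow-up is iron sufficiency, the endpoint of item (7).** The SAPs state no figure for this test, so there is none to reproduce. The following is an illustration.

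Inputs:

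- n = 150 per arm, from SAP section 2.4: "A total of 300 subjects (150 each for the MT-6548 and darbepoetin groups) should be enrolled in the treatment period".
- s, the share sufficient at a visit, is assumed to be 95%.
- u, the share on iron in screening, is assumed to be 30% to 90%. The documents give no figure.
- The two attributes are assumed independent.

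Formulas:

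- c = n(1 − u)s, sufficient and not on iron
- b = n·u(1 − s), on iron and not sufficient
- chi-square = (c − b)²/(c + b), on 1 degree of freedom

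| u | c | b | chi-square |
|---|---|---|---|
| 30% | 99.75 | 2.25 | 97.5²/102 = 93.2 |
| 50% | 71.25 | 3.75 | 67.5²/75 = 60.8 |
| 70% | 42.75 | 5.25 | 37.5²/48 = 29.3 |
| 90% | 14.25 | 6.75 | 7.5²/21 = 2.7 |

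The p-values are about 5×10⁻²² at 30%, 6×10⁻⁸ at 70% and 0.10 at 90%. An exact test on rounded counts has the same pattern: 100 against 2 gives p = 2×10⁻²⁷ at 30%, and 14 against 7 gives p = 0.19 at 90%.

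Whatever the dependence between the two attributes, c − b = n(s − u). For example, 150 × (0.95 − 0.30) = 97.5. The hypothesis tested is therefore that the share sufficient equals the share who were on iron. Change in sufficiency does not enter it.

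Dependence affects the size of the result. With the greatest possible overlap at s = 95%, u = 50% gives discordant pairs of 68 and 0 (p = 7×10⁻²¹), and u = 90% gives 7 and 0 (p = 0.016).

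**The error can also hide a change.** With s = 90% and u = 90% under independence, the discordant counts are equal (150 × 0.1 × 0.9 = 13.5 each) and p = 1.0. Sufficiency was an entry condition at screening (protocol 3.2, criterion 7; its rationale reads "Set to ensure patients without iron insufficiency"). A fall from 100% at screening to 90% would give 15 discordant pairs against 0, and an exact p of 2 × 0.5¹⁵ = 0.00006.

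**Like-for-like.** With sufficiency at both times and no net change at 95%, the expected discordant counts are 150 × 0.95 × 0.05 ≈ 7 each way if the two times are independent, so p = 1.0.

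**The case against.** The strongest reply is that this is a copying slip in a minor analysis, and most of that stands. Iron sufficiency is among the other endpoints, and protocol 13.3.2 (3) plans only incidence and ratios for discrete data of that kind. Phase 1 SAP 8.5.4.7 calls such analyses exploratory and makes no multiplicity adjustment. The proportions, their intervals and the between-group Fisher comparison in item (7) use the right variable. Item (8) tests within-arm change in ferritin and TSAT directly, with paired t-tests from the first day of the treatment period.

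Three stronger inferences are tempting, and the documents do not support them.

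- A reader might infer that the SAP definitely compares two different variables. The sentence leaves the follow-up variable unnamed, and both its baseline and its periods fit a repeat of item (6).
- A reader might infer that the p-values must be highly significant even with no change in iron status. That holds only if iron use and sufficiency differ widely. The documents do not give the share on iron, and protocol 8.5.2 requires iron to be given to maintain the criterion, so independence of use and status is also doubtful.
- A reader might infer that the Phase 1 tables are wrong. The documents do not show what was programmed.

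The reply does not rescue the sentence. On either reading it fails to test the endpoint it sits under, and a prespecified analysis should not depend on a programmer guessing the intent.

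**Conclusion.** The defect is real in the current text of both SAPs. Item (7) has no valid before-after test of iron sufficiency, because its McNemar sentence belongs to item (6). The textual finding needs no assumption.

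The numerical illustration applies only if follow-up is read as iron sufficiency. It rests on the planned 150 per arm and on assumed values for sufficiency, iron use and their dependence. Under those assumptions the p-value follows the gap between iron use and sufficiency, and it can be extreme or null regardless of any change in iron status.

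The reach is narrow: one within-arm p-value per arm and visit, for an exploratory endpoint. No primary or secondary efficacy result and no safety result depends on it.

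**What to change.** In item (7) of both SAPs:

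1. Replace the parenthesis defining baseline with the subject's own status (ferritin ≥100 ng/mL or TSAT ≥20%: yes or no) on the first day of the treatment period.
2. Replace the periods between visits with each evaluation time point.

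The first day of the treatment period is preferable to screening as baseline. The entry criterion makes nearly every subject sufficient at screening, so a test against screening could detect little but a fall.

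No new data are needed, and the change is one sentence per SAP. For Phase 1 the cost is somewhat higher. Final SAP 8.5.4.3 states that the Phase 1 analysis had already been conducted, so the sponsor should confirm which variable was programmed, correct the text by erratum, and re-run the item (7) McNemar results if the wrong variable was used. Protocol 13.4 requires the reasons for changes after data lock to be recorded and the results to be distinguished from the original plan.
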